3.6. Study Procedures

Device application: In both the ICU and non-ICU study populations, standard-of-care devices will be used in all subjects and this data will be compared to that collected using novel wearable sensors suggested in this study. After participants are consented, multiple wearable sensors (up to 5) will be placed on the participant for the duration of the study. Multiple devices are required to estimate BP. One or more devices will be placed on the chest or back, and one or more additional devices will be placed peripherally (e.g. leg, foot, arm, hand, head, or ear). One or more additional devices may be placed on the patient's respiratory support device if applicable. Placing multiple devices will allow determination of which location provides the best signals in specific populations. These devices will be placed using a medical grade skin adhesive similar to the ones used in the ICUs, which will minimize the

risk of skin irritation or allergic reaction. Alternatively, we are currently testing a “soft wrap-around device” (similar to that currently used for blood pressure monitoring in the premature babies) with a sensor. The soft wrap-around device is composed of hypoallergenic cotton. Overlying this cotton, and not touching the subject’s skin, may include Coban wraps, paper tape, or a Velcro adhesion mechanism. Given the very small size of premature infant in the NICU, we may incorporate this new technology as needed in the NICU. In the ICU population, devices will be left in place for up to 72 hours, but will either be checked by the study or clinical team to ensure skin integrity and signal quality at least once every 24 hours. In the non-ICU population, devices will be left in place for up to 3 hours during a study visit to CAMP.

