Standard of care data: In all participants where data from standard of care monitoring is captured and stored using the BedMasterEx system (all PICU and CCU beds, some NICU beds), and the Sickbay™ platform (CCU beds), this data will be used for comparison to data captured using EWP. In any participants where data are not captured and stored using the BedMasterEx system or Sickbay™ platform, video recordings will be made of the Phillips monitors using an encrypted mobile device. Within 48 hours, videos will be downloaded and transferred to a HIPAA secure server. In NICU patients without BedMasterEx data, the Somnostar system may be used to capture data for up to 4 hours of the study. All study data will be stored on an encrypted laptop and/or secure network for analysis. We will continue to follow patients for 5 years by collecting standard of care data entered into their electronic medical record.

Skin Integrity: Before and after wearable sensors are placed on the participant, the participant's skin integrity will be monitored using the ICU standard protocol, either the Braden Q scale (≥ 6 months of age) and/or Neonatal Skin Risk Assessment Scale (NSRAS; < 6 months of age). Additionally, a validated skin integrity scale will be used to score participants' skin condition at sensor placement site before sensor placement and immediately after sensor removal. At both of these time points, photographs may be taken of the participants' skin at the site of sensor placement to document any skin changes that occur during the period of wearable sensor wear. No faces will be photographed. One or more additional skin scores and photographs may be performed/taken between 30 minutes and 48 hours after sensor removal, as deemed necessary by the study and/or clinical team. The study team will consult the ICU bedside care team or CAMP clinical team within 1 hour for any concerning changes in skin integrity.

Questionnaires: After the study period ends, the parents may be approached to complete the questionnaires. These questionnaires will take less than 10 minutes to complete and are meant to assess opinions on use of these devices in the ICUs. These questionnaires will be completed using REDCap. If preferred, the family will complete a printed version of the REDCap questionnaire and this data will then be entered by study staff into the REDCap server. All questionnaire data will be stored on the secure REDCap server housed by Northwestern University.

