3.7. Study Timeline

Study recruitment, data collection, and ongoing analysis: 1-30 months
Final analysis and report preparation: 6 months

4. Study Safety

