4.1. Privacy Protections

The study team will take measures to protect the privacy and confidentiality of participants. The plan to protect patient privacy includes approaching and consenting participants in a private room. Study procedures will be done in the privacy of the patient rooms in the ICU.

Study participation discussions will be limited to members of the study staff and the involved participants.

Participant data will be coded with study identifier only. All data obtained from the bedside monitors will be stored on the Azure Cloud (maintained by Data Analytics Reporting (DAR) at Lurie Children's). All data obtained using wearable sensors will be stored on an encrypted laptop and secure network for later analysis. All questionnaire responses will be collected via Research Electronic Data Capture (REDCap) hosted by Northwestern University. When preferred, parents can fill in questionnaires on paper, and these will be transferred to REDCap by study staff after collection.

To minimize the risks, only the minimum data necessary to complete the study will be collected on each study participant.

Data to be collected include:

- Demographic data (age, gender, race, sex, gestational age (in participants <1 year of age, only))
- Body mass index, height, weight, and body surface area
- Diagnosis for admission to the ICU
- Medications during the study
- All skin integrity scores (either the Braden Q scale (≥ 6 months of age) and/or Neonatal Skin Risk Assessment Scale (NSRAS; <6 months of age) for 24 hours before, during, and 24 hours after the sensor study)
- All pain scores (Face, Legs, Activity, Cry, Consolability scale (FLACC), State Behavioral Score (SBS), Neonatal Pain, Agitation and Sedation Scale (NPASS), Neonatal Facial Coding System (NFCS))
- Alarms/clinical events during the study
- Video monitoring of patient position and movement (optional)
- Data generated by the wearable sensors and standard of care monitoring devices which will include standard physiologic measurements such as BP, HR, blood oxygenation, cerebral blood flow, pain, temperature, movement, and respiratory rate

Photographs will be labeled only by study code, and will not include subject's face. Video may include the subject's face, but all videos will be scored for position and movement within 1 month of recording, and will be deleted after scoring. All photos and videos will be stored on a password protected server accessed by a password protected computer.

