Only authorized personnel listed in the IRB application will have access to study data. The screening and enrollment log used contain the code link, and this file will be stored on the REDCap server and will have access limited to the study team. The link between the participants and their study identifier will be destroyed at the conclusion of this study, so all remaining data will be fully de-identified.

Data transferred to the study team by the NU electronic data warehouse for patients meeting screening criteria in the Prentice NICU will be downloaded onto the Lurie Children's Hospital server. This data file will be used for up to one week to allow the screening process to take place, then will be deleted.

Confidentiality will be maintained with all of the medical records of this study. Subject records will be kept in a locked cabinet, under the control of the Principal Investigator. The subject will also be assigned a code in the data sheets so that the records on the computer will be kept confidential.

Potential Risks

Data risks: The risks involved with this research are minimal and include loss of privacy and confidentiality. The safeguards in place for de-identifying and storing data should mitigate this risk. To minimize this risk, access to the data is restricted to the PI and key personnel on the research team. Data will be coded, stored without identifiers. Video data, which may include identifiable images, will be stored on an encrypted device only until position and scoring analysis take place, and will then be deleted. Data collected throughout this study will remain on the hospital network and the REDCap server, and be under the same safeguards in place for clinical data. Any data stored for future studies will be further de-identified, after study conclusion. Any data transferred off of the hospital network for statistical/data analysis will be fully de-identified before transfer.

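### Does the five-year medical-record follow-up in section 3.6 conflict with the 36-month timeline in section 3.7 in a way that needs a change to the plan?

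*Protocol*

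**What the plan says.** Section 3.6, in its paragraph on standard-of-care data, commits to long-term record collection: "We will continue to follow patients for 5 years by collecting standard of care data entered into their electronic medical record". It does not say when the five years begin.

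Section 3.7 is the only schedule. It has two lines: "Study recruitment, data collection, and ongoing analysis: 1-30 months" and "Final analysis and report preparation: 6 months". Neither mentions record follow-up, and neither says that the schedule is limited to the sensor phase.

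Section 4.1 bears on the point in two ways. It limits collection ("To minimize the risks, only the minimum data necessary to complete the study will be collected on each study participant") and then lists data items, none of which is labelled as long-term follow-up. It also says that the link between participants and their study identifier "will be destroyed at the conclusion of this study, so all remaining data will be fully de-identified". No date or event defines that conclusion.

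**The concern.** Collecting record data is data collection, and section 3.7 appears to close data collection at month 30 and the whole study at month 36. A five-year commitment cannot be met inside that window for anyone.

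The possible harm comes through the link. Record follow-up needs it. If staff took the end of the section 3.7 timeline as the conclusion of the study and destroyed the link then, the rest of the follow-up would be lost and could not be recovered. If follow-up does run its full length, the code key for up to 500 children (section 3.1) is held for years longer than the timeline suggests. In either case a reader cannot tell from section 3.7 how long linkable records are used.

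**Working it through.** **Inputs.** Follow-up: 5 years = 5 × 12 = 60 months (section 3.6). Recruitment and data collection: months 1 to 30 (section 3.7). Final analysis: 6 months (section 3.7). Sensor wear: up to 72 hours in the ICU and up to 3 hours at CAMP (section 3.6). The month of last enrolment and the start of the five-year clock are not stated, so both are varied.

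**Length of the timeline.** 30 + 6 = 36 months, if the final analysis follows directly.

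**Clock running from each enrolment.** For enrolment in month m, follow-up ends at m + 60 and passes the timeline by m + 60 − 36 = m + 24 months.

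| Enrolment month m | Follow-up available by month 36 (36 − m) | Five years reached (m + 60) | Past month 36 |
|---|---|---|---|
| 1 | 35 | 61 | 25 |
| 10 | 26 | 70 | 34 |
| 20 | 16 | 80 | 44 |
| 30 | 6 | 90 | 54 |

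**Clock running from study start.** Follow-up ends at about month 60, which is 60 − 36 = 24 months past the timeline.

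Under either clock and for any enrolment month, 60 months do not fit into 36. The arithmetic of the concern is correct.

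**What depends on the follow-up.** The next step is to look for any result that uses it.

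- Section 2.2: the primary outcome compares sensor blood pressure with standard-of-care blood pressure. The secondary outcomes are other physiologic signals, accelerometry against video, respiratory equipment and parent questionnaires. None is a long-term outcome.
- Section 5.2: the comparisons use 30-second epochs, Bland-Altman bias and precision, within-person correlations and multilevel models. All use concurrent sensor and reference data.
- Timing: "In the ICU population, devices will be left in place for up to 72 hours", and CAMP visits are shorter still. Even a patient enrolled at the very end of recruitment has complete paired data within days.

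The number of planned outcomes and analyses that use the five-year data is therefore zero. The bias, precision and correlation estimates are the same whether follow-up lasts 0, 6, 35 or 60 months.

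**The case for a change.** The strongest case for acting is that section 3.7 is headed as the timeline of the study, places data collection in months 1 to 30 without qualification and calls its last analysis final. Destroying the link cannot be undone, and a short amendment would cost little. How long children's linkable records are used should be readable from the protocol.

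Part of this stands: the scope of section 3.7 is not labelled, and the event that triggers destruction of the link is not defined. Three points limit its weight.

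First, the protocol often uses the word *study* for the sensor session. In section 3.6 the sensors stay on for the length of the study, although wear is at most 72 hours, and parents receive questionnaires once the study period is over. In section 4.1 the skin scores are timed "for 24 hours before, during, and 24 hours after the sensor study". On that usage, section 3.7 plausibly schedules recruitment, sensor data and their analysis, and the chart follow-up continues afterwards.

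Second, the data list in section 4.1 does not exclude follow-up. It is introduced as a list of what the data include, so it is open. An item such as "Alarms/clinical events during the study" may simply refer to the sensor window, and a skin-score window does not limit record follow-up. Section 5.1 separately describes extraction from the electronic health record for consented participants and sets no time limit.

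Third, the loss of the link depends on an uncharitable reading. A study that is still collecting coded record data has not concluded, so sections 3.6 and 4.1 agree when read in the ordinary way. The consent pages, which could state duration and retention, are not at hand.

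**Conclusion.** The mismatch exists, but it is a clerical one. Section 3.7 shows 36 months, while the follow-up in section 3.6 would end at about month 60 if counted from study start, or as late as about month 90 if counted from each enrolment with recruitment lasting to month 30. The overrun is therefore 24 to 54 months, depending on two facts that the protocol does not give.

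No change to the plan follows. Carried out as written, the plan gives the same primary and secondary results, because no outcome or analysis uses the follow-up and the paired measurements are finished within 72 hours. A study team would sensibly keep the link until record collection ends. Labelling the timeline or defining the end of the study would tidy the document without improving an estimate, its precision, its bias or participant safety.

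This conclusion assumes that no long-term outcome is planned in material not at hand, and that staff do not treat month 36 as the point at which the link is destroyed.

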3.7. Study Timeline

Study recruitment, data collection, and ongoing analysis: 1-30 months
Final analysis and report preparation: 6 months

4. Study Safety

4.1. Privacy Protections

The study team will take measures to protect the privacy and confidentiality of participants. The plan to protect patient privacy includes approaching and consenting participants in a private room. Study procedures will be done in the privacy of the patient rooms in the ICU.

Study participation discussions will be limited to members of the study staff and the involved participants.

Participant data will be coded with study identifier only. All data obtained from the bedside monitors will be stored on the Azure Cloud (maintained by Data Analytics Reporting (DAR) at Lurie Children's). All data obtained using wearable sensors will be stored on an encrypted laptop and secure network for later analysis. All questionnaire responses will be collected via Research Electronic Data Capture (REDCap) hosted by Northwestern University. When preferred, parents can fill in questionnaires on paper, and these will be transferred to REDCap by study staff after collection.

To minimize the risks, only the minimum data necessary to complete the study will be collected on each study participant.

Data to be collected include:

- Demographic data (age, gender, race, sex, gestational age (in participants <1 year of age, only))
- Body mass index, height, weight, and body surface area
- Diagnosis for admission to the ICU
- Medications during the study
- All skin integrity scores (either the Braden Q scale (≥ 6 months of age) and/or Neonatal Skin Risk Assessment Scale (NSRAS; <6 months of age) for 24 hours before, during, and 24 hours after the sensor study)
- All pain scores (Face, Legs, Activity, Cry, Consolability scale (FLACC), State Behavioral Score (SBS), Neonatal Pain, Agitation and Sedation Scale (NPASS), Neonatal Facial Coding System (NFCS))
- Alarms/clinical events during the study
- Video monitoring of patient position and movement (optional)
- Data generated by the wearable sensors and standard of care monitoring devices which will include standard physiologic measurements such as BP, HR, blood oxygenation, cerebral blood flow, pain, temperature, movement, and respiratory rate

Photographs will be labeled only by study code, and will not include subject's face. Video may include the subject's face, but all videos will be scored for position and movement within 1 month of recording, and will be deleted after scoring. All photos and videos will be stored on a password protected server accessed by a password protected computer.

Only authorized personnel listed in the IRB application will have access to study data. The screening and enrollment log used contain the code link, and this file will be stored on the REDCap server and will have access limited to the study team. The link between the participants and their study identifier will be destroyed at the conclusion of this study, so all remaining data will be fully de-identified.

Data transferred to the study team by the NU electronic data warehouse for patients meeting screening criteria in the Prentice NICU will be downloaded onto the Lurie Children's Hospital server. This data file will be used for up to one week to allow the screening process to take place, then will be deleted.

Confidentiality will be maintained with all of the medical records of this study. Subject records will be kept in a locked cabinet, under the control of the Principal Investigator. The subject will also be assigned a code in the data sheets so that the records on the computer will be kept confidential.

Potential Risks

Data risks: The risks involved with this research are minimal and include loss of privacy and confidentiality. The safeguards in place for de-identifying and storing data should mitigate this risk. To minimize this risk, access to the data is restricted to the PI and key personnel on the research team. Data will be coded, stored without identifiers. Video data, which may include identifiable images, will be stored on an encrypted device only until position and scoring analysis take place, and will then be deleted. Data collected throughout this study will remain on the hospital network and the REDCap server, and be under the same safeguards in place for clinical data. Any data stored for future studies will be further de-identified, after study conclusion. Any data transferred off of the hospital network for statistical/data analysis will be fully de-identified before transfer.

The clinical data and data from the wearable sensors will be collected and stored to the secure Lurie Children's Hospital server that is subject to security and access protections within the hospital intranet, including firewall and password access protection restricted to the PIs, Co-Is and study coordinators. Data will be tied to participant codes without patient identifiers. The participant code key will be maintained separately under physical (locked office) and electronic (additional password) access controls and accessible only by the PI and research team.

Skin discomfort/irritation risks: There is a risk of discomfort or irritation from adhesives and wearable sensors. It is possible that this additional sensor may contribute to skin irritation or discomfort or that the additional handling required in placing these sensors may be temporarily disruptive for the participants. Study staff and/or the clinical team will check on the participants in the ICU at least once every 24 hours to monitor for signs of discomfort, irritation, or allergic reaction. Sites of sensor placement will be assessed clinically before, immediately after removal, and at one or more additional time points (as deemed necessary by clinical team) between 30 minutes and 48 hours after removal for skin alteration by a trained member of the research team using a validated skin integrity scale. Photographs will be taken at baseline and after study; skin changes during the period of wearable sensor use or at subsequent time points will be documented photographically. If a reaction occurs, the sensor at the site will be discontinued, and the photograph will be reviewed by a member of the NICU/PICU/CICU clinical team for decision-making about management.

Photograph risks: No faces will be photographed. There is a possibility that subjects may be able to be identified from the photographs that will be taken for the study.

Video risks: Videos will be an optional part of the study, and may contain identifiable information. Videos will be stored on an encrypted device. Videos will be scored by a member of the research team for position and movement, and video will be deleted after scoring.

Survey risks: Some questions may make parents uncomfortable or upset. Participants do not have to answer these questions if they do not want to.

4.2. Discontinuation Criteria

A participant may be discontinued if the participant is unwilling or unable to tolerate the wearable sensors. Examples may include adverse reactions to the adhesive on the wearable sensors or a patient removing the wearable sensors. The bedside clinical team or family can also request discontinuation at any time. Families participating in the video monitoring can request discontinuation of the video monitoring aspect of this study at any time during the study.

4.3. Patient Withdrawal

Any participants withdrawn from the study will have the wearable sensors removed immediately. Any data collected prior to the withdrawal will remain a part of the study, and this data will be coded.

5. Statistical Analysis

5.1. Data Management and Quality Control

Clinical data will be obtained from the electronic health records for consented participants. Data will be extracted both manually and electronically from the electronic records. Data from the bedside monitors will be retrieved from the Azure cloud at Lurie Children's. The continuous data from the wearable sensors will be directly transmitted and stored on the network-encrypted laptop. Video data will be directly transmitted and stored on the same network-encrypted laptop. Continuous data measurements will be cleaned and binned by the statistical/data analyst. The cuff-based measures will be assessed by the statistical/data analyst to ensure data quality and control. Questionnaire data will be stored on the REDCap server at Northwestern University.

